Official Title: Auricular Acupressure as a Non-Opioid Adjuvant in Opioid Tolerant Patients

NCT05711537

IRB-Approved Date: 5/19/23

Title: "AURICULAR (EAR) ACUPRESSURE FOR PAIN MANAGEMENT AS A NON-OPIOID, ADJUVANT THERAPY FOR OPIOID TOLERANT PATIENTS"

Principal investigator: [name]

Co-investigator(s): [name], PhD, [name], NP, and [name], NP, [name]

Sponsor or funding source:

Wake Forest Anesthesiology Department

Background and justification for the research:

Despite recent CDC guidelines for limiting the use of opioids in non-malignant related pain, millions of Americans still rely on opioid analgesics for daily pain control. Physicians have been encouraged to seek non-opioid alternatives since there is lack of evidence for opioid efficacy in chronic pain and, even worse, serious adverse effects including dependence, respiratory suppression, and death. When chronic pain patients are admitted to the hospital due to an acute medical problem, controlling their pain becomes problematic. Physicians need to address pain levels (which are often increased), but ideally would like to do so with minimal opioids to avoid CNS and respiratory depression. At Wake Forest Baptist Health, our chronic pain team is consulted to provide safe, effective pharmacological recommendations,

There is growing evidence in the literature for efficacy of auricular acupuncture therapy for chronic pain. Auricular acupressure (AA) is a related technique that uses the same external ear points for stimulation. It is widely held that AA is relatively easy to initiate, has rare adverse effects and is accepted by patients who may have an aversion to needles. There are studies currently underway addressing use of AA in outpatient, elderly chronic low back pain patients and in the perioperative setting, however, no reports of AA as an adjunct for opioid dependent patients during hospitalization. Thus, we propose assessing the effectiveness of AA for pain control on this population via initiating it during chronic pain consults. In addition, by analyzing secondary measures and demographics we hope to characterize patients that may benefit most from AA.

Battlefield Auricular Acupressure (BAApres) Training and Intervention Fidelity
(IRB00084011)

This feasibility trial is being performed in collaboration with the BAApres Training and Intervention Fidelity study (IRB00084011). Under this grant, individual study teams conduct non-randomized feasibility trials to assess intervention feasibility and provide initial parameter estimates on specified outcomes.

The AA interventionists for this study will complete Auricular Acupressure training modules and complete competency assessments and intervention assessments throughout the study. Study teams will include the possibility that a study participant may be part of a competency assessment and that their session may be recorded and securely uploaded to a server per IRB and Institutional policies.

Objectives:

The purpose of this study is to determine if the addition of auricular acupressure to the typical pharmacological regimen given to patients on the chronic pain/addiction service will lower pain scores and decrease pain medication usage.

Setting:

This will be a study utilizing the location of Atrium Health Wake Forest Baptist (Main Campus) for initiation of study procedures.

Subject selection criteria

Any patient admitted to Atrium Health Wake Forest Baptist for which our chronic pain/addiction medicine service is consulted.

Inclusion:

Patient admitted to the hospital with a chronic pain/addiction medicine service consult.

1. Age > or equal to 18
2. History of documented chronic pain with or without opioid use disorder
 - a. Polysubstance abuse or opioid use disorder
 - b. **Or opioid use (documented as home medication)**
3. Expected length of stay (admission) is at least 5 days at the time of recruitment
4. Able to read and understand the informed consent form

Exclusion:

1. Patient refusal
2. Patients who are at a risk of leaving against medical advice (AMA) during their current admission may be excluded per the investigator's discretion
3. Since this is a feasibility pilot, only English-speaking participants will be eligible.
4. Inability to communicate via telephone
5. Participants with a history of skin disease (e.g., psoriasis) involving the ear, adhesive allergy, recent scar tissue on ear, or current abrasions or cuts on ear,
6. Cognitive impairment (delirium, dementia)
7. Physical impairment preventing them from applying pressure to the beads
8. Patients with cardiac pacemakers (contraindication to POINTER PAL)

9. Use of some types of hearing aids (obstructing the placement of beads)
10. Any chronic or acute illness or psychiatric conditions that would impact adherence to the study requirements

Sample Size

A total of 20 patients will be recruited from chronic pain patients hospitalized at Wake Forest Baptist Health Main Campus

Interventions and Interactions:

- A. The chronic pain Advanced Practice Provider will evaluate the patient and determine if and when they can be included in the study. If the patient is determined to be eligible, the participant will be consented by a study team member prior to collection of any study data.

Baseline

- Review the home dose of opioid w/ participant collecting type, frequency and milligram use and date and time of last use prior to admission.
- A study team member will provide the participant with the study questionnaire packet as well as instructions for completing the questionnaires.
- Participants will be informed of the reminders that they will receive to complete the questionnaires twice a day for three days (i.e., verbal reminder from staff, signage placed in the room). Participant contact information will be collected to ensure appropriate and timely follow up.
- A study team member will perform the pain score assessment with the participant to establish baseline pain score.
- The participants will be asked to complete baseline questionnaires prior to the initiating placement of the acupressure including: Discomfort on Initiation of Acupressure (on 0-10 NRS scale), Pain Intensity, Enjoyment, General Activities Scale (PEG), Pain Catastrophizing Scale (PCS), Generalized Anxiety Disorder Scale (GAD-7), Patient Global Impression of Change Scale (PGIC) (only collected after Acupressure applied) and PROMIS sleep disturbance scale.

Day 1

The Baseline and Day 1 visits can take place on the same day.

Following completion of baseline questionnaires, the trained Auricular Acupressure nurse will place the acupressure pads and instruct the participant how to do acupressure three times daily for 3 days.

- o If the ear contains lesions, skin breakdown, or show signs of irritation, the acupressure pads will not be placed, and this will be noted in the study record.

- If the participant consented to the recording portion of the study, they will be reminded of the process and the acupressure nurse will confirm that the participant still agrees to participate in the recording portion of the study.
- A total of 10 adhesive acupressure pads will be placed, 5 acupressure pads per ear. The pads will be placed bilaterally on the following 5 auricular sites: 1) “Cygulate gyrus”, 2) “Thalamus”, 3) “Omega 2”, 4) “Point Zero”, and 5) “Shen Men”. These sites were selected based on the WV’s Battlefield Auricular Acupressure Protocol for acute and chronic pain. This is the protocol the Veterans Administration uses for acupressure therapy for acute and chronic pain management.
- Each ear will be cleansed with alcohol, beginning at the base of the ear (lobule) to the apex. The acupoints will be visually located and marked with a sterile surgical marker or a POINTER-PAL trigger point locator will be used if one is available.
- The acupressure pads will be placed by visual identification of the preselected acupoints as per BAA protocol. The pads will be placed on the identified site by hand or with the assistance tweezers, with the seed portion of the pad aligning with the identified acupoint.
- To secure the pad, gentle but firm pressure will be applied to the pad, making sure that pressure is applied to the entire pad.
- After placement, the study nurse will apply moderate pressure to each acupressure pad for 30 seconds (total time 2.5 minutes per ear). Both right and left ear site will be stimulated at the same time with pressure in the following order: 1) “Cygulate gyrus”, 2) “Thalamus”, 3) “Omega 2”, 4) “Point Zero”, and 5) “Shen Men”.
- Participants will tell the acupressure nurse when they feel a tingling sensation in the ear or feel moderate tenderness or pressure as confirmation that moderate pressure is being applied.
- The acupressure nurse will document acupressure pad placement and activation in Wake One.
 - If the acupressure pads fall off before day 3 the participant will be instructed to note which pad fell off in the study participant questionnaire. The acupressure pads will not be replaced during the study.
- After completion of the day 3 study activities, the study team will instruct the participant to remove the acupressure pads by gently pulling on the edges of the pad and lifting off with their fingers or using tweezers to loosen the pad if needed.

The interventionist (Acupressure nurse) may record and take pictures of the treatment visit. These recordings will be used to ascertain fidelity to the intervention protocol as it relates to a) proper placement of acupressure seeds and b) and provision of instructions to the participant.

Each study participant will be asked to sign a separate consent giving permission for the intervention to be recorded and used for educational and research purposes. The recordings will be done to limit exposure of the study participant’s face.

The interventionist's time will be measured in minutes from time the interventionist enters room to place acupressure pads to when the interventionist exits room. Qualitative questions will be used to assess overall feasibility.

- The study team will perform the pain score assessment with participants (on 0-10 NRS scale) two (2) times a day for 3 days. If the study team is unable to perform the pain scores assessment in person, we will use the pain score that has been assessed by the clinical team as part of their regular care and documented in the participant's medical record.

Study participants will be reminded to complete their daily study activities.

- A member of the study team will remind the participant to complete their assessment(s) or the study nurse can place an order in Wake One to prompt the care team to remind the participant.
- A sign will be placed in the participant's room reminding them to complete their study activities.

Monitoring opioid usage: data abstraction will be done and verified in Wake One if the participant remains inpatient for the 3 days.

End of Study Assessment:

Within 24 hours of the completion of the assessments and the removal of the acupressure beads, a member of the study team will assess patients'

- Pain scores
- Opioid medication frequency and dosage
- Verify completion of Day 3 study questionnaires: Pain Catastrophizing Scale (PCS); Generalized Anxiety Disorder Scale (GAD-7); Pain, Enjoyment, General Activities Scale (PEG); Patient Global Impression of Change Scale (PGIC); PROMIS sleep disturbance scale

Participant will also be asked to complete "Willingness or desire to decrease opioid dependence and usage" and Acupressure Acceptability questionnaires on Day 3

Outcome Measures:

Since this is a feasibility study, results will be analyzed initially using descriptive statistics of main outcome measures.

To evaluate the efficacy of the auricular acupressure the following outcomes will be assessed:

Primary Outcomes:

Patient reported pain scores – change in patient reported pain scores (derived from the NRS and PEG scale) from baseline and Day 1-Day 3.

Secondary Outcomes to be measured:

Opioid use - Pre-Admission Opioid requirement and change from baseline (medication used during the intervention and as reported afterwards vs. home dose before the study started) collecting type, frequency and milligram use and date and time of last use prior to admission measuring mean/median changes from Baseline to Day 3 post evaluation. Trajectory of am and pm pain scores.

Generalized Anxiety Disorder Scale (GAD-7) – A Self-administered 7 item scale that draws from DSM-V criteria for General Anxiety Disorder (GAD) to identify GAD and measure symptom severity. It is routinely used as a tool to measure longitudinal changes and track treatment progress.

Patients are asked to rate the frequency of anxiety symptoms over the last 2 weeks on a Likert Scale (0-3). In general, patients with GAD or other common anxiety disorders exhibit GAD-7 scores of 10 or greater.

Pain Catastrophizing Scale (PCS) - The assessment of thoughts and feelings of the patients will be assessed using questions that are rated 0 for not at all to 4 for all the time. The Pain Catastrophizing Scale (PCS) assesses the extent of catastrophic thinking due to low back pain according to 3 components: rumination, magnification, and helplessness. It is a 13-item scale, with a total range of 0 to 52. Higher scores are associated with higher amounts of pain catastrophizing.

Composite Pain, Enjoyment and General Activity Scale (PEG) Assessment of pain intensity and interference. We will compare scores before and after initiation of Auricular Acupressure.

Patient Global Impression of Change (PGIC) – patient reported assessment of improvement or decline of their pain

PROMIS Sleep disturbance – patient reported outcome on the quality of their sleep.

Acupressure Acceptability questions - We will ask acceptability questions. "How satisfied were you with how your pain has been treated?" using the Likert scale to measure "Very satisfied =5, Satisfied=4, Somewhat satisfied = 3, Somewhat dissatisfied= 2, Dissatisfied 1, Very Dissatisfied 0. Would you consider using auricular acupressure in the future for pain or if recommended by your nurse or physician? a. No, would not use again (Score of 0) b. Maybe (Score of 1), c. Yes, I would consider using in the future (Score of 2) 3. Is there anything else you would like to tell us that may be helpful for us to know regarding ear acupressure? (Each answer will be collected and assessed for future studies).

Willingness or desire to decrease opioid dependence and usage (Assessed using Likert Scale). Assessment of patient's willingness or desire to decrease opioid dependence and usage will be assessed through having the patient answer by stating (1) Strongly disagree; (2) Disagree; (3) Neither agree nor disagree; (4) Agree; (5) Strongly agree to determine patients with a higher score denoting a greater willingness to decrease dependence.

BAA Press placement survey (interventionists only)

The Interventionist's (Acupressure nurse) will be asked to capture time related to completion of study tasks and other qualitative questions to assess overall feasibility.

Additional Data collection: contact information, relevant demographic data that will be recorded are DOB, age, gender identity, sex at birth, BMI, ethnicity/race, educational level, employment status, relationship status, disability insurance status and socioeconomic status. Relevant medical history will be duration of narcotic use (in years) and comorbid pain syndrome diagnoses.

Study activity	Baseline ^a	Day 1	Day 2	Day 3/ end of study
Informed Consent signed	X			
Review the home dose of opioid w/ participant	X			
Complete data collection form	X	X	X	X
Distribute Participant Questionnaire and review completion instructions	X			
Administer or record Pain score assessment (NRS) ^b	X	X	X	X
Questionnaire completion reminder ^c		X	X	X

Pain Catastrophizing Scale (PCS)	X			X
Pain, Enjoyment, General Activities Scale (PEG)	X			X
Patient Global Impression of Change Scale (PGIC)	X			X
PROMIS sleep disturbance scale	X			X
Generalized Anxiety Disorder Scale (GAD-7)	X			X
Acupressure placement and patient education		X		
*Optional interventionist recording of AA placement ^d		X		
Willingness or desire to decrease opioid dependence and usage questionnaire				X
Acupressure Acceptability questionnaire				X
Study team collect completed questionnaire				X
Compensation administration				X

BAA press placement survey (interventionist only)	X	X	X	X
---	---	---	---	---

^a Baseline and Day 1 can be completed on the same day. Baseline activities are to be completed prior to Acupressure administration

^b The study team will perform the pain score assessment with the participant two times a day for three days. If the study team is unable to perform the pain scores assessment in person, the pain score that has been assessed by their clinical team as part of their regular care will be pulled

^c Participants will receive reminders to complete the study questionnaires twice a day

^d Only participants who agree to participate in the optional recording/photography at the time of informed consent will have their acupressure placement session recorded

Analytical Plan

Sample Size:

This is a feasibility study with no control group. Target enrollment is 20 participants. Data from this study will be used to generate parameter estimates to calculate power for future studies.

Analysis Plan:

Since this is a feasibility study, results will be analyzed initially using descriptive statistics of main outcome measures. Any group comparisons will be done using chi square tests for proportions, and t-tests or ANOVA procedures for continuous variables. Other inferential statistical analysis will be conducted as appropriate.

Human Subjects Protection

Subject Recruitment Methods

Any patient who is on the chronic pain/addiction consult service be approached by either Primary Investigator or study staff regarding participation. Only eligible patients willing to complete all survey's pre and post procedures and provide written consent will participate. If eligible, the participant will be consented by study personnel in their private hospital room. If a family member or visitor is present, the study team member will ask the participant permission to discuss the study at that time or if they would prefer to discuss another time. The study team will ensure that the participant understands the voluntary nature of participating in the research study and that study participation study will not affect the care that they will receive.

The study personnel will maintain a record of eligible study participants separate from the study files. This list will include name, MRN, and hospital room number and

enrollment status. The list will be kept in a secure file on a secure computer, separate from the study files and only accessible to study staff. The file of eligible participants will be destroyed at the end of recruitment.

Informed Consent

Signed informed consent will be obtained from each subject prior to any study procedures being performed. Any study related procedures will adhere to ICH-GCP standards.

Confidentiality and Privacy

Confidentiality will be protected by collecting only information needed to assess study outcomes, minimizing to the fullest extent possible the collection of any information that could directly identify subjects, and maintaining all study information in a secure manner. To help ensure subject privacy and confidentiality, only a unique study identifier will appear on the data collection form. Any collected patient identifying information corresponding to the unique study identifier will be maintained on a linkage file, stored separately from the data. The linkage file will be kept secure, with access limited to designated study personnel. Following data collection subject identifying information will be destroyed 3 years after the completion of the study consistent with data validation and study design, producing an anonymous analytical data set. Data access will be limited to study staff. Data and records will be kept locked and secured, with any computer data password protected. No reference to any individual participant will appear in reports, presentations, or publications that may arise from the study.

Data and Safety Monitoring

The principal investigator will be responsible for the overall monitoring of the data and safety of study participants. The principal investigator will be assisted by other members of the study staff. Although no serious safety events have been reported in the literature related to auricular acupressure, participants will be asked to report any events to study personnel. Participants and the acupressure nurses will be instructed to monitor and report any concerns to the principal investigator.

Reporting of Unanticipated Problems, Adverse Events or Deviations

Any unanticipated problems, serious and unexpected adverse events, deviations or protocol changes will be promptly reported by the principal investigator or designated member of the research team to the IRB and sponsor or appropriate government agency if appropriate.

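### The NRS part of the primary outcome is an uncontrolled change from one baseline reading at no fixed hour, and nothing planned shows whether pain was already falling before the pads went on.

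*Combined protocol and SAP*

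**What the plan says.** All references are to the combined protocol and SAP.

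- **Baseline reading.** Interventions and Interactions, Baseline: "A study team member will perform the pain score assessment with the participant to establish baseline pain score". No repeat, averaging or clock time is given.
- **Timing relative to placement.** Under Day 1: "The Baseline and Day 1 visits can take place on the same day". Footnote a of the study activity table adds: "Baseline activities are to be completed prior to Acupressure administration". No minimum interval is set.
- **Timing relative to the consult.** The background proposes to assess acupressure "via initiating it during chronic pain consults". Interventions and Interactions lets the provider "determine if and when they can be included in the study".
- **Expected pain level.** Background: "Physicians need to address pain levels (which are often increased), but ideally would like to do so with minimal opioids".
- **Follow-up readings.** NRS twice a day for 3 days, so up to 6 readings. A score charted in routine care is accepted when the study team cannot take one. Footnote b repeats this. It is attached to a table row that includes Baseline, but it covers three days and sets no second pre-placement reading.
- **Outcomes.** The primary outcome is change in pain scores derived from the NRS and the PEG, introduced as a way to evaluate efficacy. A secondary item is "Trajectory of am and pm pain scores".
- **Analysis.** The Analytical Plan states that there is no control group, targets 20 participants, begins with descriptive statistics, leaves inferential tests open, and intends the estimates for future power calculations.

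**The concern.** With no comparison group, the change from baseline is the whole of the evidence on pain, and every participant's change rests on one pre-placement score. Three things other than acupressure can move it. Pain may already be coming down after an acute admission. A morning baseline may be set against an evening follow-up. The single reading also carries its full reading-to-reading error.

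A fourth, regression from a chance high, arises only if patients tend to enter when a reading happens to be high.

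At stake is how the descriptive result can be read. The mean change is presented under an efficacy aim, and the mean and SD of change are natural inputs to the later power calculations. As written, the plan collects nothing that shows the level or direction of NRS pain before placement beyond that one score.

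**Working it through.** The plan has no figure to reproduce. The target of 20 has no SD, effect size, alpha or power behind it. Every input below is an assumption apart from n = 20, the single baseline reading and two readings on Day 3. The Day 3 NRS is taken as the mean of its two readings, which the plan does not specify.

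**1. Settling.** Assume a natural fall of 0.25 to 0.5 points a day. Baseline to Day 3 is 2 days if Baseline and Day 1 coincide, and 3 days if Baseline is the day before.
- Low: 0.25 × 2 = 0.5 points.
- High: 0.5 × 3 = 1.5 points.

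If such a fall were tested with a two-sided 5% paired t-test at n = 20, the chance of significance with no acupressure effect (noncentral t, 19 df) would be:

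| Natural fall | SD of change 2.0 | 2.5 | 3.0 |
|---|---|---|---|
| 0.5 | 0.186 | 0.136 | 0.109 |
| 1.0 | 0.565 | 0.397 | 0.294 |

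**2. Time of day.** Assume an am/pm difference of 0.5 to 1.5 points. A morning baseline set against an evening follow-up shifts the change by that amount. Against the mean of one am and one pm reading the shift is half, 0.25 to 0.75. If baseline hours vary between patients, the shifts partly cancel in the mean but add to the SD.

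**3. Regression from a chance high.** Expected fall = (1 − ρ) × SD × φ(z)/q, where q is the upper share of readings that leads to entry.
- No selection on the reading: 0.
- q = 0.5, SD 2.0, ρ = 0.8: 0.2 × 2.0 × 0.798 = 0.32 points.
- q = 0.5, SD 2.5, ρ = 0.5: 0.5 × 2.5 × 0.798 = 1.00 point.

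The documents set no NRS threshold, so q is unknown and this term may be zero.

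**4. Would averaging earlier readings help precision?** With independent errors, SD of change = √(τ² + s²(1/k + 1/2)), where s is the within-patient reading SD, τ the SD of true change and k the number of baseline readings. For s = 1.5, τ = 1.0:
- k = 1: √(1 + 2.25 × 1.5) = √4.375 = 2.09.
- k = 4: √(1 + 2.25 × 0.75) = √2.6875 = 1.64, a reduction of 22%.

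Over s = 1.0 to 2.0 and τ = 0.5 to 1.5, the reduction is 10.6% to 27.9%.

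Readings hours apart are unlikely to have independent errors. With error correlation 0.5 within each window, the mean of m readings has error variance s²(1 + 0.5(m − 1))/m:
- k = 1: √(1 + 2.25 + 1.6875) = √4.9375 = 2.22.
- k = 4: √(1 + 1.40625 + 1.6875) = √4.09375 = 2.02, a reduction of about 9%.

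**5. What averaging does to bias.** Four readings spread over the 24 hours before placement centre about 12 hours earlier. If pain is falling 0.25 to 0.5 points a day, their mean lies 0.125 to 0.25 points above the level at placement, and the apparent fall grows by that amount.

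**The case against.** The strongest reply is that this is a 20-patient feasibility study that openly declares no control group and leads with descriptive statistics. The largest figure above, settling, comes from the lack of a comparison group, and no choice of baseline removes it. That stands. It limits what the fix can claim, but it does not make the pre-placement course uninformative.

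A reader might infer more than the documents support:

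- **That baseline is taken at the consult, when pain is at its peak.** The background speaks of starting during consults, but the provider decides whether and when a patient enters. The remark on raised pain describes admitted chronic pain patients in general. The service also covers addiction medicine, so a consult need not mark a pain peak.
- **That regression to the mean certainly inflates the change.** Without a pain threshold for entry, its size is unknown and may be zero.
- **That the am/pm trajectory cannot be formed.** Day 1 to Day 3 can be compared am with am and pm with pm from the planned readings. Only a time-matched comparison with baseline is missing for one of the two.
- **That the whole primary outcome is affected alike.** It also uses the PEG, scheduled once at Baseline and once on Day 3. The reading-to-reading and time-of-day arguments apply mainly to the NRS.
- **That a 24-hour mean should replace the baseline.** Step 5 shows that this enlarges the apparent fall when pain is settling, and step 4 shows that the precision gain may be small.
- **That the SD of change is wrong.** An SD based on one baseline reading is the right input for a later trial that also uses one.

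The data collection form is listed only by title in Appendix A. It may already capture reading times or earlier scores, and this cannot be judged from the text.

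**Conclusion.** The point holds in a limited form, as a cheap improvement and not a flaw that undermines a feasibility study. The NRS change is uncontrolled, starts from one reading at an unfixed hour, and may begin the same day as placement in patients whose pain is often raised. Settling, time of day and single-reading error can enter it.

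Under the assumed rates, settling alone could account for 0.5 to 1.5 points. Time of day could add or subtract up to 0.5 to 1.5 points in an am-to-pm comparison. Regression from a chance high cannot be sized. The precision gain from averaging is about 22% or about 9% in the central case, depending on whether reading errors are independent or correlated at 0.5.

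The documents do not support saying that the planned change is biased by a known amount. They support saying that, as written, the study could not show whether pain was already falling.

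**What to change.** 1. Keep the study-team NRS reading nearest placement as the main baseline and record its clock time.
2. After consent, abstract from Wake One all charted NRS scores, with times, from the 24 hours before placement, or since admission if that is shorter. Flag the source of each score.
3. Report the pre-placement change (first to last score) beside the Day 1 to Day 3 change.
4. Show am-to-am and pm-to-pm comparisons with baseline wherever a matching pre-placement score exists.
5. Show the change from the mean of pre-placement readings only as a sensitivity result, and say that this mean sits above the level at placement if pain is already falling.
6. State that the pre-placement series makes settling visible but does not separate it from an acupressure effect.

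The cost is one extra chart abstraction per participant, 20 in all, from a record the study already uses, plus a few lines in the outcome definition. It needs no extra visit and no delay to placement. The downside is that charted scores are collected less uniformly than study-team scores, which is why the source should be flagged.

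### Does the primary pain outcome need rewriting because PEG appears in both outcome tiers and no single NRS change is named?

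*Combined protocol and SAP*

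**What the plan says.** Under Outcome Measures, the protocol opens with "To evaluate the efficacy of the auricular acupressure the following outcomes will be assessed" and gives the primary outcome as "change in patient reported pain scores (derived from the NRS and PEG scale) from baseline and Day 1-Day 3". The next heading is "Secondary Outcomes to be measured". The list under it includes "Composite Pain, Enjoyment and General Activity Scale (PEG) Assessment of pain intensity and interference", compared before and after acupressure starts. The same list contains the trajectory of morning and evening pain scores, and opioid use with its window stated: "measuring mean/median changes from Baseline to Day 3 post evaluation".

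The schedule of study activities marks NRS at Baseline and Days 1, 2 and 3, and PEG at Baseline and Day 3 only. Its footnote b says "The study team will perform the pain score assessment with the participant two times a day for three days". Footnote a lets Baseline and Day 1 share a day but requires that "Baseline activities are to be completed prior to Acupressure administration". The End of Study Assessment adds pain scores taken within 24 hours of completing assessments and removing the beads.

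The Analytical Plan describes a feasibility study of 20 participants with no control group. It starts with descriptive statistics, and the data are to supply parameter estimates for powering later studies. It states no alpha, power, effect size or SD.

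**The concern.** Three things look wrong. First, PEG change sits in both tiers, and no rule says whether NRS and PEG are separate primaries or one combined score. Second, the primary window mentions Days 1 to 3, but PEG is not collected on Days 1 and 2. Third, twice-daily NRS over three days gives six readings. The last reading, the Day 3 mean and the mean of all six, each minus baseline, all fit the wording.

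Two things would be at stake. A report could choose the most favourable version after the data are seen and still follow the protocol. The mean and SD of change, which are meant to feed later power calculations, also differ with the definition.

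**Working it through.** **No plan figure to reproduce.** The target of 20 comes with no calculation. What follows compares the passages and then works an illustration on assumed inputs.

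**Passages side by side.**
- PEG at Baseline and Day 3 yields one change score per patient, and the End of Study Assessment has Day 3 PEG completion verified. The primary wording does not require daily PEG values, so the schedule does not contradict it.
- The Primary Outcomes heading is plural and names two instruments. Two separate primary measures is therefore a natural reading, though not an explicit one.
- The am/pm trajectory is secondary, which gives the repeated NRS series a place outside the primary outcome.
- What remains is PEG listed twice and an unnamed NRS summary.

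**How much the NRS summary matters.** Assume unit variance at each reading, one baseline and six later readings. The documents give no correlations, so take either a common correlation r, or correlation decaying by a factor of 0.7 to 0.95 per reading.

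With common correlation r, the variance of change is:
- last reading: 2(1−r)
- Day 3 mean: 1 + (1+r)/2 − 2r = 1.5(1−r)
- mean of six: 1 + (1+5r)/6 − 2r = (7/6)(1−r)

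A later sample size is proportional to variance ÷ (mean change)². If the effect is immediate and flat, the mean changes are 1, 1 and 1. If pain falls steadily, they are 1, (5/6+1)/2 = 0.917 and 21/36 = 0.583.

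Under common correlation:
- last versus mean of six: flat 2 ÷ (7/6) = 1.71; steady 1.714 × 0.583² = 0.58
- Day 3 mean versus mean of six: flat 1.5 ÷ (7/6) = 1.29; steady 1.286 × (0.583/0.917)² = 0.52

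Across all the correlation patterns assumed:

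| Comparison (ratio of later N) | Flat effect | Steady fall |
|---|---|---|
| Last reading vs mean of six | 1.71 to 2.31 | 0.58 to 0.78 |
| Day 3 mean vs mean of six | 1.29 to 2.03 | 0.52 to 0.82 |
| Last reading vs Day 3 mean | 1.13 to 1.33 | 0.95 to 1.12 |

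A steady fall reaching 2.0 points at the last reading would be reported as 2.0, 2.0 × 0.917 = 1.83, or 2.0 × 0.583 = 1.17.

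**Set against the precision available.** At n=20 the 95% half-width for a mean change is t(19; 0.975)/√20 = 0.47 SD. The 95% limits for the SD are 0.760 and 1.461 times the estimate. Squared, they put a later N between 0.58 and 2.13 times its estimated value, whichever summary is used.

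**Post-hoc choice.** Simulation used 40,000 trials with n=20, no true change and one-sample t tests on change at an assumed two-sided 5%. The chance that at least one of the three NRS changes is significant is 8% to 9%. Adding a PEG change, correlated 0.3 to 0.7 with the Day 3 NRS change, raises it to 11% to 14%. These rates apply only if such tests are run and one is selected, and the plan specifies neither.

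**The case for a change.** The strongest case for a change is that the protocol says these outcomes evaluate efficacy and that its data will power later studies. An SD of change cannot be used until the change is defined, and even descriptive results must be labelled primary or secondary. Two or three sentences would settle it, with no new data.

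Much of this stands. PEG is listed twice, no NRS summary is named, and naming one would be tidier. It does not show that the plan as written leads to an unsound result. The readings are all collected, so a later trial can choose its endpoint and compute the matching SD from these data. With no control group, a significant before-after change would not establish efficacy whichever summary was used.

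The obvious repair is to make the Day 3 NRS mean primary and PEG secondary. That has its own costs: it loses precision if the effect is flat, and it removes interference from the primary outcome. Nothing in the documents favours that choice over keeping two primaries. It also leaves two questions open: whether the end-of-study pain score counts as a Day 3 reading, and whether the baseline score is one of Day 1's two readings when both fall on the same day. If it is, there are five post-placement readings and not six.

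**Conclusion.** No change to the plan follows. Listing PEG in both tiers is a clerical overlap. The unnamed NRS summary is a gap that an analyst fills by reporting NRS and PEG changes separately, each with its mean, SD, baseline and time point stated. Choosing one summary in advance is a fair trade-off with no clear winner: the ratio of later sample sizes runs from 0.52 to 2.31, and its direction turns on whether the effect is immediate or gradual. Those ratios rest on assumed equal variances, assumed correlations and six post-placement readings. The 8% to 14% error rates rest further on tests and an alpha that the plan does not set. In a 20-patient, single-arm, descriptive-first study, the ambiguity affects how results are labelled and not whether they are sound.
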